7.5 Replacements

Participants who withdraw or are withdrawn from the study within 1 week of randomisation may be replaced in order to have approximately 60 participants provide at least 7 days of post baseline data.

8. Study Assessments and Procedures

- Study procedures and their timing are summarised in the SoA (section 1.3). Protocol waivers or exemptions are not allowed.
- Immediate safety concerns should be discussed with the sponsor immediately upon occurrence or awareness to determine if the participant should continue or discontinue study intervention.
- Adherence to the study design requirements, including those specified in the SoA, is essential and required for study conduct.
- All Screening evaluations must be completed and reviewed to confirm that potential participants meet all eligibility criteria. The investigator will maintain a screening log to record details of all participants screened and to confirm eligibility or record reasons for screening failure, as applicable.
- Procedures conducted as part of the participant's routine clinical management (e.g. blood count) and obtained before signing of the ICF may be utilised for screening or baseline purposes provided the procedures meet the protocol-specified criteria and were performed within the time frame defined in the SoA. Likewise, procedures conducted as part of the participant's routine clinical management may be utilised for any of the study data provided the procedures meet the protocol-specified criteria and were performed within the time frame defined in the SoA.
- The maximum amount of blood collected from each participant over the duration of the study, for the purposes of the study, including any extra assessments that may be required, will not exceed 140mL. Repeat or unscheduled samples may be taken for safety reasons or for technical issues with the samples.
- Repeat or unscheduled visits may be conducted at the investigator's discretion but all details must be recorded in the CRF.

8.1. Efficacy Assessments

Planned timepoints for all efficacy assessments are provided in the SoA. This data can be collected from the patient's medical records if performed at the same time-point, and need not be repeated for research purposes. Where possible, all assessments will be taken from those performed as part of the participant's routine clinical care.

8.1.1. Oxygen Saturation

Oxygen saturation will be measured using a peripheral pulse oximeter and will also be analysed as a ratio with the oxygen flow ($\text{SpO}_2 / \text{FiO}_2$). The measurement will ideally be performed with the subject sitting and having been rested for at least 10 minutes.

If the subject is on 3litres/min oxygen flow or less, and the investigator feels it is safe to do so, the investigator will remove the subject's supplemental oxygen for 10 minutes while they remain seated, and while continuously monitoring the oxygen saturation. After 10 minutes the oxygen saturation reading will be taken to calculate the S/F ratio on room air. If, during this process, the saturations drop by greater than 4%, the oxygen will be immediately replaced and the ratio measured on oxygen.

8.1.2. WHO Ordinal Scale

The WHO ordinal scale will be collected throughout the study. This is an accepted instrument which has been developed specifically for trials in patients with COVID-19.

Figure 3: WHO ordinal scale for clinical improvement (OSCI) of COVID-19

Patient State	Descriptor	Score
Uninfected	No clinical or virological evidence of infection	0
Ambulatory	No limitation of activities	1
	Limitation of activities	2
Hospitalized Mild disease	Hospitalized, no oxygen therapy	3
	Oxygen by mask or nasal prongs	4
Hospitalized Severe Disease	Non-invasive ventilation or high-flow oxygen	5
	Intubation and mechanical ventilation	6
	Ventilation + additional organ support – pressors, RRT, ECMO	7
Dead	Death	8

8.1.3 Participant Questionnaire and Diary

When participants are discharged, they will be given a daily questionnaire and diary to complete. The purpose is to record if the participant changes their current medications, starts taking any new medication, whether they are on home oxygen therapy, whether they continue to have COVID-19 symptoms, and whether these symptoms interfere with their usual activities (to enable calculation of the OSCI score) and to record any adverse events.

These questionnaires and diary should be completed once daily, until the patient is symptom free and off oxygen therapy for at least 48 hours, or until Day 42 (whichever is sooner).

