*If a patient is discharged then these assessments may not be performed.

@Whilst an inpatient, participants should have a daily assessment for evidence of nausea, vomiting, diarrhoea, bloating and abdominal pain. This information will be collected for outpatients in the patient questionnaire.

& If a participant is not discharged at Day 14 and remains in hospital, Day 14 assessments will be performed until a participant is discharged from hospital or they reach the final follow-up visit (Day 42).

¹ Pregnancy test will only be performed in women of child-bearing potential (Appendix 2).

² If the patient is on 3L/min oxygen flow or less, this assessment should be performed after the patient is at rest on room air for 10 minutes, as detailed in section 8.1.1.

³ If the patient is discharged prior to these blood tests, where possible outpatient blood testing will be organised.

⁴ Extraction of relevant clinical data from the patient's medical record (such as but not limited to symptoms, concomitant medications, other relevant blood tests, and radiology reports such as chest radiograph or CT scan).

⁵ If the patient is discharged, they will be given a daily questionnaire to complete; a telephone call will be made on day 7, 14, 21 and 42 (telephone call has a window of +/- 1 day).

⁶ The patient will be asked to continue to fill the questionnaire daily until their symptoms have fully resolved for 48 hours or until the day 42 telephone visit (whichever is earlier).

⁷ This is an optional sample for research purposes but will be collected whenever possible once at the Baseline visit and then again once between Days 5-14. If the patient is discharged prior to this faecal test, where possible, an outpatient sample will be collected.

⁸ Administered twice daily for six doses) and then once daily for the remaining days (17 doses total). Treatment will be stopped if the participant is admitted to ICU, meets individual stopping criteria, or is withdrawn from the study.

⁹ Smoking status to include whether current-smoker, ex-smoker, or never-smoker; and to quantify current usage and total pack-year history.

2. Introduction

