5.3.2.8 Daily Diary Compliance

The daily diary should be completed on every day following discharge from hospital until the participant has reported at least two consecutive days with no symptoms (Q1) and a return to their usual activities (Q3).

The last day on which a daily diary is expected is defined as the earliest of the second consecutive day on which the participant reported no symptoms and a return to their usual activities and Day 42/Study day of early withdrawal from the study.

The number of days on which a daily diary is expected will be defined as:

Number of diary days expected = Date of last expected diary day – Date of discharge

The number of diary days completed will include all days on which at least questions 1-3 of the diary were answered up to and including the date of the last expected diary day. Diary days completed after Day 42 or after the second consecutive day with no symptoms and a return to their usual activities will not be included.

Daily diary compliance will be calculated as:

Daily diary compliance (%) = $100 \times \text{Number of diary days completed} / \text{Number of diary days expected}$

Daily diary compliance will be presented to 1 dp in the listings.

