5.3.3.4 WHO OSCI

The WHO OSCI has values ranging from 0 to 8 as shown in [Table 6](#).

Table 6 WHO Ordinal Scale for clinical Improvement

Participant State	Descriptor	Score
Uninfected	No clinical or virological evidence of infection	0
Ambulatory	No limitation of activities	1
	Limitation of activities	2

Participant State	Descriptor	Score
Hospitalized – Mild disease	Hospitalized, no oxygen therapy	3
	Oxygen by mask or nasal prongs	4
Hospitalized – Severe Disease	Non-invasive ventilation or high flow oxygen	5
	Intubation and mechanical ventilation	6
	Ventilation + additional organ support	7
Dead	Death	8

The WHO OSCI will be recorded daily in the eCRF while participants remain in hospital. Once discharged, the WHO OSCI will be derived from questions 1 and 2 of the daily COVID-19 diary using the rules defined in [Table 7](#).

Table 7 Derivation of WHO OSCI using the Outpatient Daily Covid-19 diary

Question 1: Overall, how severe were your COVID-19 symptoms today?	Question 2: How much did your COVID-19 symptoms interfere with your usual activities today?	WHO OSCI Score
No COVID-19 symptoms today	Any response	0
Mild, moderate, severe or very severe	Not at all	1
Mild, moderate, severe or very severe	Somewhat or Very much	2

For participants who report question 1 as “No COVID-19 symptoms today” and a return to their usual activities (Q3) for 2 days in a row do not need to complete the COVID-19 diary on subsequent days. If this condition is met, the missing WHO OSCI score will be imputed as 0 for any remaining study days up to and including Day 42.

Note that participants who are discharged on home oxygen will still be considered as having WHO OSCI score =2 as the participant state is considered before the descriptor in [Table 6](#).

For participants who die, the WHO OSCI score will be imputed to 8 for all remaining study days after death.

WHO OSCI scores that are missing for reasons other than death or full recovery of symptoms will not be imputed.

For the secondary endpoint looking at whether participants remained at or below their baseline WHO OSCI score at Days 4, 7, 10, 14, 21 and 42, participants who show an increased score and then return to their baseline score (or lower) will not be considered as having met the criterion for this endpoint. Only participants who have not reported a score above their baseline score on any day prior to the endpoint day will be considered as having met the endpoint for that day.

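### Protocol and SAP set different diary stop rules, so some recovered participants who stop as the protocol directs may have no OSCI score at later days

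*Protocol*

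**What the plan says.** The documents give three versions of when a discharged participant may stop the daily diary, each with Day 42 as the outer limit.

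- **Protocol 8.1.3:** the diary runs "until the patient is symptom free and off oxygen therapy for at least 48 hours". Symptoms and oxygen both count; usual activities do not.
- **Protocol 1.3, Schedule of Activities footnote 6:** it runs "until their symptoms have fully resolved for 48 hours". Oxygen is not mentioned. The telephone reminder in protocol 8.1.4 and the design summary in SAP 5.1 also refer to symptom resolution only.
- **SAP 5.3.3.4:** participants who report no symptoms on Q1 "and a return to their usual activities (Q3) for 2 days in a row do not need to complete the COVID-19 diary" after that. SAP 5.3.2.8 uses the same Q1-plus-Q3 condition for the last expected diary day. Neither section has an oxygen condition.

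Imputation follows the SAP's version: "If this condition is met, the missing WHO OSCI score will be imputed as 0 for any remaining study days", up to Day 42. The closing rule in the same section is looser: "WHO OSCI scores that are missing for reasons other than death or full recovery of symptoms will not be imputed". SAP 9.3.3.1 adds that OSCI data missing for reasons other than the listed intercurrent events are not imputed, and SAP 8 bases percentages on the non-missing sample size. SAP 14 records no changes to the protocol.

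**The concern.** After discharge the SAP derives OSCI from the diary, so the stop rule decides who has a score at later days. A participant can meet the protocol's rule, stop, and still fail the SAP's condition for carrying 0 forward. That participant's last scores are 0, the best on the scale, and the later days are then missing. The missingness depends on outcome, and it shifts the later OSCI distribution toward sicker participants.

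Q3 has no part in scoring. SAP Table 7 uses Q1 and Q2 and gives a symptom-free day a 0 whatever the answer on interference with activities. Scores would be lost through a question that does not determine the score.

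Oxygen differs in the opposite direction. Under the SAP, a symptom-free participant still on home oxygen could stop and be carried forward as 0, while protocol 8.1.3 keeps that participant on the diary.

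**Working it through.** No figure in the plan depends on this point, so there is none to reproduce. The check compares the rules and then applies the SAP's own formulas to an assumed participant.

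**Rules side by side**

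| Source | No symptoms | Off oxygen | Usual activities (Q3) |
|---|---|---|---|
| Protocol 8.1.3 | yes, 48 h | yes, 48 h | no |
| Protocol footnote 6 | yes, 48 h | no | no |
| Protocol 8.1.4, SAP 5.1 | yes | no | no |
| SAP 5.3.2.8, 5.3.3.4 | yes, 2 days | no | yes, 2 days |

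**Assumed participant.** Discharged Day 7, symptom free and off oxygen on Days 10 and 11, diary completed on Days 8-11 and then stopped as protocol 8.1.3 allows.

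Formulas from SAP 5.3.2.8: days expected = last expected diary day − discharge day; compliance = 100 × days completed / days expected. Days completed = 4.

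- Q3 met on both days: expected = 11 − 7 = 4; compliance = 4/4 = 100%; OSCI imputed as 0 for Days 12-42.
- Q3 not met: the last expected day becomes Day 42, so expected = 42 − 7 = 35; compliance = 4/35 = 11.4%. OSCI is not imputed for Days 12-42, which is 42 − 11 = 31 days and includes Days 14, 21 and 42.

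**Range for the group.** The documents do not give the share f of participants who stop without Q3. For f from 0% to 30% of 60 participants, the number is 60f: 0 at 0%, 3 at 5%, 6 at 10%, 12 at 20% and 18 at 30%.

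Suppose the true share at OSCI 0 on a given day is 70% (assumption) and everyone lost is truly at 0. The observed share among those with a score is (0.70 − f)/(1 − f):

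- f = 5%: 0.65/0.95 = 68.4%
- f = 10%: 0.60/0.90 = 66.7%
- f = 20%: 0.50/0.80 = 62.5%
- f = 30%: 0.40/0.70 = 57.1%

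**Which endpoints are reached.** The loss affects the OSCI percentages by day, the CMH tests at those days, the shift tables, the at-or-below-baseline proportion and diary compliance. Time to recovery (SAP 5.3.3.6) uses the first score of 0 with no later increase, and that score is recorded before the diary stops. The primary S/F endpoint, overall survival, ventilation-free survival and time to discharge do not rest on diary scores after recovery. In the pyrexia sensitivity rule (SAP 5.3.3.8) the same Q3 condition appears, but failing it leads to carrying the last fever response forward, not to a missing day.

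**Home oxygen.** Table 7 gives 0 for a symptom-free day. A note in the same section scores participants discharged on home oxygen as 2. A symptom-free participant on home oxygen fits both.

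**The case against.** The strongest reply is that little may be lost in practice. Anyone who reports both Q1 and Q3 on two consecutive days is imputed as 0 through Day 42. The diary form is not in the documents; if it tells participants to continue until Q3 is met, the affected group could be close to empty. The closing rule in SAP 5.3.3.4 exempts full recovery of symptoms from non-imputation, without naming Q3, so a programmer could impute these participants. All analyses are described as descriptive, in a pilot. Declining to carry 0 forward for a month for someone not back to usual activities is also a defensible caution.

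Most of this stands as a limit on size. It does not remove the mismatch. The two sentences in SAP 5.3.3.4 support different datasets, so two programmers could produce different Day 21 and Day 42 tables. The cautious reading sits poorly with Table 7, which has already scored those days as 0. The Schedule of Activities does list the ordinal scale at Days 21 and 42, but the SAP takes outpatient scores from the diary, and the stated purposes of the telephone call do not include OSCI.

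A reader might infer that recovered participants who follow the protocol lose their OSCI scores as a class. The SAP does not support that: only those without Q3 on two consecutive days are at risk. A reader might also infer a biased treatment comparison. The rule is the same in both blinded arms, and nothing in the documents shows that the loss would differ between them.

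**Conclusion.** The stop rules disagree across the protocol and SAP, and the protocol also disagrees with its own footnote on oxygen. Under the SAP's explicit condition, some participants who stop as protocol 8.1.3 directs would have missing, unimputed OSCI at later days despite last scores of 0, and low diary compliance. The closing rule leaves this ambiguous.

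The size is unknown and may be small. The range of 0-18 participants rests on an assumed 0-30% of 60. The fall in the observed share from 70% to between 68.4% and 57.1% further assumes a true 70% at OSCI 0, 5-30% lost, and everyone lost truly at 0. The consequence is limited to the secondary by-day OSCI summaries and diary compliance. It is worth settling before database lock because the correction is cheap and the missingness depends on outcome.

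**What to change.** 1. In SAP 5.3.2.8, 5.3.3.4 and the matching pyrexia rule in 5.3.3.8, drop the Q3 condition. After two consecutive diary days with no symptoms (Q1) and no oxygen therapy, count the diary as complete and, in 5.3.3.4, impute OSCI as 0 to Day 42. Tie the closing non-imputation sentence in 5.3.3.4 to this same condition.
2. Align Schedule of Activities footnote 6 and protocol 8.1.4 with protocol 8.1.3, and check that the diary form carries the same instruction. Otherwise the mismatch returns for symptom-free participants on home oxygen who stop under the footnote.
3. State one OSCI score for symptom-free participants still on home oxygen, reconciling Table 7 (0) with the note in 5.3.3.4 (2), so that they are neither missing nor carried forward as 0 by default.

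The cost is short edits to three SAP sections and two protocol places. No new data item is needed: SAP 5.3.3.7 already has oxygen changes after discharge transcribed from the diary to the oxygen therapy page of the CRF.

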8.1.4 Telephone call

If patients are discharged, they will be contacted by telephone on days 7, 14, 21 and 42 (+/- 1 day). The purpose of this call is to seek reporting of AEs, remind the participant to continue to fill their daily questionnaire (until symptoms have resolved or Day 42, whichever is sooner), and to offer the opportunity for any study-related questions.

8.2. Safety Assessments

Planned timepoints for all safety assessments are provided in the SoA.

8.2.1. Physical Examinations

- A physical examination will include, at a minimum, assessments of the cardiovascular, respiratory, and GI systems. Height and weight will also be measured and recorded. The physical examination data will be recorded from the admission record and medical notes where possible.

8.2.2. Vital Signs

- Blood pressure, pulse rate, respiratory rate, oxygen saturations and temperature will be assessed.

8.2.3. Strain-specific PCR for EDP1815

- Plasma samples will be taken from participants at day 7, to assess for the presence of EDP1815 levels by PCR with strain-specific primers that can detect EDP1815 specifically, even when other strains of *Prevotella Histicola* are present.
- If a participant has a positive blood culture for *P. histicola* identified as part of their clinical care, then isolates will be tested for the EDP1815 strain.

Note: the study will be paused, and dosing held in all participants while identifying the specific strain of *P. histicola*.

8.2.4. Gastrointestinal Assessment

- Inpatients will have a daily assessment for evidence of any severity of nausea, vomiting, diarrhoea, bloating and abdominal pain. This will be recorded as an adverse event and an assessment of causality will be made.
- Outpatients will complete the daily diary card (section 8.1.3), where they will be prompted to record GI side-effects such as nausea, vomiting, diarrhoea, bloating and abdominal pain as AEs.

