6.1. Study Interventions Administered

All study interventions in this study will be administered orally. EDP1815 will be supplied as capsules that are enteric coated to release the contents in the duodenum and jejunum. The drug product is manufactured by [REDACTED].

The EDP1815 drug product is available as enteric coated hydroxylpropyl methylcellulose (HPMC) hard capsules in white to off-white color. The formulation of EDP1815 consist of freeze-dried powder of *P. histicola* and excipients. The excipients include mannitol, magnesium stearate and colloidal silicon dioxide. Each EDP1815 PIC contains 8.0×10^{10} cells of *P. histicola*.

The matching placebo are identical in appearance but do not contain *P. histicola* or any other bacteria. Matching placebo is supplied by [REDACTED]. The placebo excipients include microcrystalline cellulose and magnesium stearate.

Treatment with EDP1815 or placebo will be twice daily for 6 doses and then once daily for 11 doses (14-day total course). There should be a minimum of two hours between the twice daily doses. For subjects who are discharged within the 14-day period, medication will be dispensed to take at home.

Table 3: Treatment Arms

Arm	Dosage
EDP1815	1.6 x 10^{11} cells as 2 capsules twice daily for 6 doses, then once daily to 14 days
Placebo	2 capsules twice daily for 6 doses, then once daily to 14 days

Participants must refrain from consuming acidic drinks 1 hour either side of dosing and from eating 2 hours before dosing and 1 hour after dosing. Refer to the Pharmacy Manual for further details.

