10.3.1 Adverse Events of Special Interest

TEAEs of nausea, vomiting, diarrhea, bloating and abdominal pain will be considered as adverse events of special interest (AESI).

AESI will be summarized by treatment, preferred term, and CTCAE grade. The summary will contain the number and percentage of participants and the number of events.

AESI will also be summarized by treatment, preferred term and relationship to study drug in the same manner.

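### Daily GI prompting of discharged participants can end before home dosing does, because the diary stops on COVID-19 recovery and not on the last dose

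*Protocol*

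**What the plan says.** **Dosing.** The course is 17 doses over 14 days, six at twice daily and then eleven at once daily (Protocol 6.1; SoA footnote 8). It carries on after discharge: "For subjects who are discharged within the 14-day period, medication will be dispensed to take at home" (Protocol 6.1).

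**GI collection.** Inpatients are assessed every day for five named GI symptoms, from nausea to abdominal pain. For outpatients, Protocol 8.2.4 says: "Outpatients will complete the daily diary card (section 8.1.3), where they will be prompted to record GI side-effects". SoA footnote @ agrees: "This information will be collected for outpatients in the patient questionnaire". No other tool with a GI prompt is named for outpatients.

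**When the diary stops.** Protocol 8.1.3 says: "These questionnaires and diary should be completed once daily, until the patient is symptom free and off oxygen therapy for at least 48 hours", or Day 42 if that comes sooner. Protocol 8.1.4 and SoA footnote 6 refer to symptom resolution without the oxygen condition. SAP 5.3.2.8 says that the diary "should be completed on every day following discharge from hospital until the participant has reported at least two consecutive days with no symptoms" and, in addition, a return to usual activities. SAP 5.1 and 5.3.3.4 repeat a recovery-based stop, and the pyrexia rules in SAP 5.3.3.8 rely on it.

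**Use of the data.** The five GI symptoms are the adverse events of special interest (AESI; SAP 10.3.1). They are the only non-serious events below Grade 3 that reach the CRF (Protocol 8.3; SAP 10.2). GI events of any grade are a stated focus of the DMC's safety review at every interim (SAP 7.4.2), and the AESI tables go to every DMC meeting unblinded (SAP Appendix 1).

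**The concern.** The diary has two jobs: tracking COVID-19 recovery and collecting GI side-effects of a drug that is still being taken. Its stop rule serves only the first. The question behind the SAP's stop rule asks about COVID-19 symptoms (SAP 5.3.3.4, Table 7). A participant who recovers soon after discharge can therefore put the diary away with days of dosing left.

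Two things are at stake. First, the GI events reported so far are of the kind that is easily lost: Protocol 2.4 describes earlier adverse events as mild and transient, and diarrhoea is among them. Second, the length of prompted observation depends on recovery, which the trial hopes to speed up. If the arms recover at different rates, the AESI table compares arms that were observed in different ways.

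The planned compliance summary would not reveal the gap. Under SAP 5.3.2.8, expected diary days end at the second symptom-free day and later entries are not counted, so a participant can score 100% with several doses unprompted.

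**Working it through.** **1. The plan's own dose count.** 3 days × 2 + 11 days × 1 = 17 doses, as in SoA footnote 8. At two capsules per dose this is 34, which agrees with SAP Table 3: 2 × (14 + 3) = 34.

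**2. Longest gap.** Inputs: the diary starts the day after discharge and needs two consecutive reported symptom-free days (SAP 5.3.2.8); dosing runs to Day 14 (Protocol 6.1). With discharge on Day D and no symptoms from the next day, the last diary day is D + 2. The number of dosing days without a diary is then 14 − (D + 2) = 12 − D. Each further day of symptoms after discharge shortens the gap by one.

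| Discharge day | Gap if symptom-free at once | Share of 17 doses | Gap if symptoms last 2 more days | Gap if symptoms last 4 more days |
|---|---|---|---|---|
| 4 | 8 days | 8/17 = 47% | 6 | 4 |
| 5 | 7 days | 7/17 = 41% | 5 | 3 |
| 7 | 5 days | 5/17 = 29% | 3 | 1 |
| 10 | 2 days | 2/17 = 12% | 0 | 0 |
| 12 | 0 | 0% | 0 | 0 |

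Dosing is once daily on all the gap days in the table, also for participants who receive a single dose on Day 1 (SAP 5.3.2.7), so gap days equal doses.

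**3. What remains in the gap.** Calls are made on Days 7, 14, 21 and 42, each ± 1 day (Protocol 8.1.4). They seek adverse events, with no GI prompt stated, and Protocol 8.3.2 prefers open-ended questions. The Day 7 and Day 14 calls can be 13 − 8 = 5 to 15 − 6 = 9 days apart. The second can fall on Day 13, before the last dose.

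**4. Illustration of the effect on the comparison.** None of these inputs is in the documents. Assume the same daily chance h of a first GI event in both arms, a last prompted day L of 7 for everyone in a faster arm and 10 for everyone in a slower arm, full capture while prompted, and a share s of later first events recovered by the calls. The proportion recorded by Day 14 is

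1 − (1 − h)^L + s × (1 − h)^L × [1 − (1 − h)^(14 − L)].

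For h = 2% and s = 0 this gives 1 − 0.98^7 = 13.2% against 1 − 0.98^10 = 18.3%. With 30 per arm (60 randomised 1:1), that is 1.53 fewer participants in the faster arm. The range, faster against slower arm, with the shortfall out of 30 taken before rounding:

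| h | True rate by Day 14 | s = 0 | s = 0.5 | s = 0.8 | s = 1 |
|---|---|---|---|---|---|
| 1% | 13.1% | 6.8% vs 9.6% (0.83) | 10.0% vs 11.3% (0.42) | 11.9% vs 12.4% (0.17) | equal (0) |
| 2% | 24.6% | 13.2% vs 18.3% (1.53) | 18.9% vs 21.5% (0.77) | 22.3% vs 23.4% (0.31) | equal (0) |
| 4% | 43.5% | 24.9% vs 33.5% (2.60) | 34.2% vs 38.5% (1.30) | 39.8% vs 41.5% (0.52) | equal (0) |

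**The case against.** **Other routes exist.** The calls are made partly to collect adverse events, and the Day 14 call falls close to the end of dosing. GI events of any grade must be recorded (Protocol 8.3). Grade 3 and 4 GI events trigger dosing rules (Protocol 7.2) and are unlikely to pass unnoticed. This stands. A reader might infer that GI events after the diary stops are missed; the documents do not support that. The change is from daily prompted reporting to periodic recalled reporting, and the risk lies with mild, short events. The daily adverse-event review in the SoA is a weaker defence, because that row carries the asterisk footnote under which assessments may lapse after discharge.

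**The SoA may already cover dosing.** In the questionnaire row, footnote 6 is attached only to the last three marks, and the earlier daily marks carry no stop condition. That can be read as an unconditional diary to about Day 13, and Protocol Section 8 makes adherence to the SoA mandatory. If so, the problem is a conflict between the SoA and both Protocol 8.1.3 and SAP 5.3.2.8. The column placement is uncertain because the table was extracted from PDF: the telephone row appears shifted by one column. Either reading calls for reconciliation.

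**Bias between arms is not shown.** A reader might infer that the AESI comparison favours EDP1815. That needs both faster recovery on EDP1815 and incomplete capture by the calls, and the documents give no figure for either. A participant who attributes GI complaints to COVID-19 keeps the diary going, which narrows the gap. The study is a pilot with descriptive analyses only.

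**Long gaps may be uncommon.** All participants need oxygen at baseline. A gap of 8 days requires discharge by Day 4; at Day 4 it also requires immediate freedom from symptoms, with the oxygen or usual-activities condition met. This also stands.

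**Conclusion.** The point holds as a gap in ascertainment. As Protocol 8.1.3 and SAP 5.3.2.8 are written, daily prompted GI collection in outpatients can end up to 12 − D dosing days before the last dose. The 47% of doses for discharge on Day 4 is close to a worst case, and the gap closes for discharge from Day 12. These figures rest only on the stated schedule and on symptoms being absent from the day after discharge.

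The consequence is possible under-recording of mild, short GI AESIs. Any difference between arms is conditional. Under the assumed inputs above it ranges from 0 with full recall to 2.6 participants of 30 with no recall at h = 4%; it is 0.2 to 0.5 of 30 if the calls recover 80% of later events. These values illustrate sensitivity and do not estimate a bias in this trial. The change is worth making because the affected data are a named DMC safety output and the correction is cheap.

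**What to change.** State in Protocol 8.1.3 and 8.1.4, SoA footnote 6 and SAP 5.3.2.8 that the diary's adverse-event and GI items are completed daily from discharge through the day of the last dose (Day 14 if the course is completed), whatever the symptom status. The symptom-resolution stop applies only after that.

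Make the SoA questionnaire row and its footnote marks show the same rule. In SAP 5.3.2.8, count expected days for these items through the last dose so that compliance reflects the dosing period.

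Align SAP 5.1, 5.3.3.4 and 5.3.3.8, which state or rely on the same stop. Keep the OSCI and pyrexia imputation rules tied to symptom resolution, so that the efficacy derivations do not change.

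A lighter alternative is a scripted GI question at the existing Day 7 and Day 14 calls. It restores the prompt but not daily reporting, and would need to be squared with the preference for open-ended questioning in Protocol 8.3.2.

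Cost: wording in the protocol, diary instructions and SAP, plus a few short diary days for early recoverers (at most 8 for discharge on Day 4). No new instrument or visit is needed, and no dose or clinical rule changes.
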